## 1. Study Synopsis

Protocol Title:	Assessment of the effect of Positive Airway Pressure on energy and vitality in mild Obstructive Sleep Apnea patients. The Merge Study.
Protocol Short Title:	The Merge Study
Patient Population:	Apnea Hypopnoea Index (AHI) 5-15 events/hour as per American Academy of Sleep Medicine (AASM) 2007 scoring criteria (or AHI $\geq 5$ per AASM 2012 if AHI 0-4 per AASM 2007)
Study Design	A prospective randomised parallel trial with 3 months of active treatment versus a control arm
Purpose of clinical trial:	To determine the benefits of Continuous Positive Airway Pressure (CPAP) therapy in patients with mild Obstructive Sleep Apnea (OSA)
Primary Objective:	To determine the changes in quality of life (energy and vitality) from baseline (pre-treatment) to 3 months post CPAP initiation in patients with mild OSA (as per AASM 2012 criteria ), compared to controls
Secondary Objectives	
 
1. To determine the changes in quality of life (on a range of measures) from baseline (pre-treatment) to 3 months post CPAP initiation in patients with mild OSA (as per AASM 2012 criteria), compared to controls
 
2. To determine changes in quality of life (on a range of measures) from baseline (pre-treatment) to 3 months post CPAP initiation in patients with mild OSA (as per AASM 2007 criteria), compared to controls
 
3. Comparison of automated scoring and manual review (as per AASM 2012 criteria)
 

Trial Design	Prospective randomised open-label controlled trial
Endpoints:	
Primary Endpoint: A Change in the Energy and Vitality Dimension of the SF-36 questionnaire from baseline (pre-treatment) to 3 months post CPAP initiation in mild OSA patients (AASM 2012 criteria), compared to controls
 
Secondary endpoints
 
 
1. Change in outcomes between baseline (pre-treatment) and 3 months post CPAP initiation in mild OSA patients (AASM 2012 criteria) compared to controls in a number of quality of life measures: 
 
- Short Form 36 (SF 36)
 
- Epworth Sleepiness Scale (ESS)
 
- Fatigue Severity Scale (FSS)
 
- Functional Outcomes of Sleep Questionnaire (FOSQ)
 
- Hospital Anxiety and Depression Scale (HADS)
 
- Insomnia Severity Index (ISI)
 
- Health Questionnaire (EQ5D)
 
 
 
2. Change in outcomes between baseline (pre-treatment) and 3 months post CPAP initiation in mild OSA patients (AASM 2007 criteria) compared to controls in a number of quality of life measures: 
 
- Short Form 36 (SF 36)
 
- Epworth Sleepiness Scale (ESS)
 
- Fatigue Severity Scale (FSS)
 
 
 

	
 
- Functional Outcomes of Sleep Questionnaire (FOSQ)
 
- Hospital Anxiety and Depression Scale (HADS)
 
- Insomnia Severity Index (ISI)
 
- Health Questionnaire (EQ5D)
 
 
3. Comparison of automated scoring and manual review of scoring (as per AASM 2012 criteria)

Sample Size:	224 (112 per group)
Summary of eligibility Criteria:	
Study Inclusion Criteria
 
 
• Aged <math>\geq 18</math> and <math>\leq 80</math> years
 
• Ability and willingness to provide written informed consent
 
• AHI 5-15 events/hour as per AASM 2007 scoring criteria (or AHI <math>\geq 5</math> per AASM 2012 if AHI 0-4 per AASM 2007)
 
• Ability to tolerate a one hour long CPAP run in test
 
 
Exclusion Criteria:
 
 
• The presence of unstable cardiac disease
 
• Inability to give fully informed consent
 
• Supplemental oxygen
 
• Secondary sleep pathology e.g. Periodic Limb Movement Syndrome, Narcolepsy, Circadian Disorder, Obesity Hypoventilation Syndrome
 
• ESS <math>\geq 15</math>, or concerns about sleepy driving from physician/ sleep lab staff
 
• BMI <math>\geq 40</math> Kg/m^2
 
• Previous CPAP usage
 

Intervention:	Continuous Positive Airway Pressure (CPAP)
Study Duration per subject:	3 months

### 3. Introduction

#### 3.1. Background

Obstructive sleep apnea (OSA) is classified into three groups based on the number of breathing events sufferers experience per hour (known as the apnea hypopnoea index (AHI)). The classifications are: mild (AHI 5-15), moderate (AHI 16-30) and severe (AHI >30).

The effects of moderate and severe OSA are well documented. In the short term, moderate to severe OSA is known to cause excessive daytime sleepiness, motor vehicle accidents, impaired cognitive function and reduced quality of life. It has also been associated with serious health consequences such as hypertension, cardiovascular morbidity and mortality, stroke and diabetes. Effective treatment with continuous positive airway pressure (CPAP) has been shown to improve symptoms and reduce health risks in these patients.

Mild OSA has not been as extensively studied. Although there is a reasonable pool of evidence that suggests that even minor sleep related breathing disturbances are associated with negative consequences, there is no consensus on when treatment should be initiated or, indeed the best treatment for the patients. The few randomised controlled trials (RCT) reviewing CPAP use in these patients have yielded mixed results, potentially due to methodology issues. Two well-designed, adequately powered RCT's in mild OSA patients include the CATNAP and MOSAIC Clinical Trials.

The rationale for the CATNAP study was to understand the effect of CPAP on daily functioning in patients with daytime sleepiness (ESS >10) and mild to moderate OSA (AHI 5-30). Patients were randomised to receive either CPAP treatment or placebo (Sham CPAP) for a period of 8 weeks. The primary outcome was the FOSQ questionnaire, and 223 patients completed the trial. The investigators found a significant improvement in daily functioning in the active CPAP group compared with the placebo group.

What remained unclear following the CATNAP study was whether mild OSA patients without excessive daytime sleepiness would also benefit from CPAP treatment. The MOSAIC trial aimed to answer this question in an RCT of 391 mild patients who were diagnosed with OSA (Oximetry Disturbance Index (ODI) >7.5/h), but with symptoms at a level not severe enough to warrant treatment by conventional guidelines. Patients were randomised to receive either CPAP therapy or standard care for 6 months. The investigators found that CPAP improved daytime sleepiness (based on ESS scores); objective sleepiness; and self-assessed health status (SF36), but not vascular health risk.

The CATNAP and MOSAIC clinical trials suggest that treating mild OSA is beneficial for patients, however despite this evidence treatment for mild OSA is not consistently offered.

**In 2012, the American Academy of Sleep Medicine (AASM) changed the criteria needed to score a hypopnoea during a sleep study.** Previous 2007 criteria had required a hypopnoea to include a decrease in oronasal airflow by  $\geq 30\%$  from baseline, an event of at least 10 seconds, and  $\geq 4\%$  SpO2 desaturation. These criteria had been widely accepted by healthcare providers to form the basis of reimbursement for patient equipment. In 2012, a change was made to these criteria which permitted hypopnoeas to be scored with an arousal only, or an oxygen desaturation of  $\geq 3\%$ .

Recommended Hypopnoea Definition:	
AASM 2007	
 
• A decrease in oronasal airflow by <math>\geq 30\%</math> from baseline AND
 
• The event is <math>\geq 10</math> sec long AND
 
• Associated with <math>\geq 4\%</math> SpO2 desat
 

AASM 2012	
 
• A decrease in oronasal airflow by <math>\geq 30\%</math> from baseline AND
 
• The event is <math>\geq 10</math> sec long AND
 
• Associated with <math>\geq 3\%</math> SpO2 desat OR arousal
 

The AASM updated their criteria as they felt that patients who suffer from frequent respiratory events and arousals from sleep, but insufficient to cause hypoxia, and therefore not meeting the older AASM 2007 criteria, may benefit from treatment. This change in rules significantly increases the percentage of patients who may now be diagnosed with OSA, potentially by up to 40%.

However, the new scoring rules remain controversial as there is no compelling evidence that patients with mild OSA according to this new criteria benefit from treatment. As a result, health insurance reimbursement rules in some countries have not adopted the 2012 criteria. **No adequately powered RCTs have shown the benefits of CPAP treatment in this expanded group of mild OSA patients.**

In summary, there are two current issues regarding the treatment of mild sleep apnea:

- 1) There is not universal agreement on whether treatment of mild OSA, as scored by the commonly used AASM 2007 criteria is necessary. Indeed, some countries have limited reimbursement for OSA to only moderate and severe patients
- 2) The newer criteria of OSA defined by the AASM in 2012 are broader, and increase the potential OSA population by up to 40%. The criteria were expanded due to growing clinical evidence that this newly defined mild OSA has detrimental effects on quality of life and cognitive performance. However, there is no objective evidence that treating these patients with CPAP is beneficial. Therefore, this new criteria has not been widely adopted.

### 3.2. Rationale for this study

The primary focus of this study is mild OSA as per the AASM 2012 criteria. We wish to prospectively determine the response to CPAP in patients presenting with mild OSA (AHI 5-15) when scored using the AASM 2012 criteria. As there is no clear evidence regarding the benefits of treatment in this group of patients, this study will provide future guidance for physicians, and policy makers on how to best manage these patients. Our primary objective for this study is to analyse the changes in quality of life from baseline to 3 months post CPAP initiation in mild OSA patients (AASM 2012) compared with a control group.

A secondary focus of this study is mild OSA as per the AASM 2007 criteria. Because an AASM 2012 criterion has not been universally adopted into clinical practice, many healthcare systems are still using AASM 2007 criteria. Although some evidence exists of the benefits of treating mild OSA when scoring as per AASM 2007 criteria, more evidence is required. As part of this proposed study, we wish to add to this pool of knowledge by analysing the quality of life improvements of CPAP in patients diagnosed using the AASM 2007 criteria as a secondary endpoint.

In addition, previous studies have focused on the use of daytime sleepiness as a measure of CPAP success. It is our clinical experience that many mild patients complain of symptoms other than sleepiness (e.g. fatigue, depression, lack of energy, restless sleep etc.). Therefore, we have designed this study to measure the CPAP response in a way which may be more applicable to these patients. The study primary endpoint is the Energy and Vitality dimension of the SF 36, as this has consistently shown to be the most sensitive dimension of the SF 36 for measuring quality of life improvements in mild OSA patients.

## 4. Objectives

### 4.1. Study Objectives

#### Primary Objective:

1. To determine the changes in quality of life (energy and vitality) from baseline (pre-treatment) to 3 months post CPAP initiation in patients with mild OSA (**as per AASM 2012 criteria**), compared to untreated controls.

#### Secondary Objectives:

1. To determine the changes in quality of life (on a range of measures) from baseline (pre-treatment) to 3 months post CPAP initiation in patients with mild OSA (**as per AASM 2012 criteria**), compared to untreated controls
2. To determine changes in quality of life (on a range of measures) from baseline (pre-treatment) to 3 months post CPAP initiation in patients with mild OSA (**as per AASM 2007 criteria**), compared to untreated controls
3. Comparison of automated scoring and manual review (as per AASM 2012 criteria)

### 4.2. Study Endpoints

#### 4.2.1. Primary Endpoint

A Change in the Energy and Vitality Component of the SF 36 questionnaire from baseline (pre-treatment) to 3 months post CPAP initiation in mild OSA patients (**scored with AASM 2012 criteria**) compared to control subjects.

#### 4.2.2. Secondary Endpoints

[figure not shown]
1. Change in outcomes between baseline (pre-treatment) and 3 months post CPAP initiation in mild OSA patients (**scored with AASM 2012 criteria**) compared to controls in a number of quality of life measures:
  - Short Form 36 (SF 36)
  - Epworth Sleepiness Scale (ESS) (8 scales, and 2 [physical and mental composite] domains)
  - Fatigue Severity Scale (FSS)
  - Functional Outcomes of Sleep Questionnaire (FOSQ)
  - Hospital Anxiety and Depression Scale (HADS)
  - Insomnia Severity Index (ISI)
  - Health Questionnaire (EQ5D)
2. Change in outcomes between baseline (pre-treatment) and 3 months post CPAP initiation in mild OSA patients (**scored with AASM 2007 criteria**) compared to controls in a number of quality of life measures:
  - Short Form 36 (SF 36) (8 scales, and 2 [physical and mental composite] domains)
  - Epworth Sleepiness Scale (ESS)
  - Fatigue Severity Scale (FSS)
  - Functional Outcomes of Sleep Questionnaire (FOSQ)
  - Hospital Anxiety and Depression Scale (HADS)
  - Insomnia Severity Index (ISI)
  - Health Questionnaire (EQ5D)
  - 
  - 3. Comparison of automated scoring and manual review of scoring (as per AASM 2012 criteria)
  -

### 4.3. Study Design Overview

A prospective randomised parallel trial with 3 months of active treatment versus a control arm

## 5. Study Methods

### 5.1. Pre Study Screening

[Figure 1]

Patients who visit a participating local sleep service for an overnight sleep test will be screened for the study. Screening will involve the use of the Apnealink home sleep test. The home sleep test can be done instead of, or as well as, routine patient screening. The Apnealink is a 5 channel recording device which is undertaken in the patients home (see section 0). The Apnealink contains automatic scoring software which provides the clinician with an AHI (scored as per AASM 2007) of the screening night.

A successful study is one where at least 4 hours have been recorded and all signals are working correctly (see Section 0.) If a study is not successful, the participant will be contacted by the local sleep service and asked if they would like to re-do the screening Apnealink home sleep test.

Participants are entered into the study based on automatic AASM 2007 scoring. Those who meet either of the following criteria are eligible to continue:

- Mild OSA (AHI 5–15) shown on an ApneaLink Air home sleep test (scored as per AASM 2007);
- No OSA (AHI 0–4.9) shown on the ApneaLink Air home sleep test (scored as per AASM 2007), however rescoreing with AASM 2012 shows an AHI  $\geq 5$  (see section 5.1.2)

### 5.1.2. Participants with no OSA (AHI 0-5) scored with AASM 2007

Participants whose home sleep test shows no OSA (AHI 0-4.9; AASM 2007) may still be eligible to enter the study if, when the study is rescored using AASM 2012 scoring criteria, they have an AHI  $\geq 5$ . In this case, these participants' sleep studies will be expedited for rescored with AASM 2012 scoring criteria before commencing study activities. If rescored with AASM 2012 criteria shows no OSA (AHI  $< 5$ ), the participant will be excluded from the study

### 5.2. Apnealink AirView account

Participants who may wish to take part in the study will have their home sleep test uploaded to the ApneaLink AirView account. Before the participant's ApneaLink Air data is uploaded, the study will be discussed with participants, they will be provided the *Participant Information Sheet* and participants will give written *Informed Consent*.

Data from the ApneaLink Air can be uploaded and stored on a cloud based system known as AirView (see section 0). For the purpose of this study, a dedicated AirView account will be set up for study participants only. Access to this account will be restricted to only those in the study team.

### 5.3. Home Sleep Test Scoring Review

Following on from participant enrolment in the study, all ApneaLink Air home sleep tests will be rescored using automated software, based on AASM 2012, criteria by ResMed Ltd (Sydney). The AHI provided by this automated AASM 2012 scoring will be the AHI used in the primary study objective. The AHI provided by automated AASM 2007 scoring will be the AHI used for secondary study objectives.

The algorithm for AASM 2007 automated scoring has been commercially available for many years and has been validated in many studies. The automated AASM 2012 algorithm is newly developed at ResMed, and is being concurrently validated. All automated scoring by AASM 2012 criteria will be reviewed by an expert Central Scorer. The AHI provided by the Central Scorer will be reported as a secondary study outcome.

As the primary outcome of the study relates to mild OSA as per AASM 2012, it may seem more intuitive to screen and enrol using this criterion. This has not been done for two reasons:

- 1) Treatment for Mild OSA as per AASM 2007 scoring is not routinely reimbursed due to a lack of evidence. We wish to add to this pool of knowledge by including AASM 2007 mild OSA as a secondary endpoint.
- 2) A home sleep test which scores using AASM 2012 (including arousals) is not commercially available at the time of writing this protocol. However, during the course of the study this technology is being validated and expected to be available at the time of study completion.

## 5.4 Study Visits

### 5.4.1. Study Visit 1

[figure not shown]

Figure 2: Study Flowchart

Participants will attend their local sleep service for Study Visit 1. The inclusion criteria will be checked (*Inclusion Checklist CRF*). As part of the inclusion criteria participants will complete a one hour CPAP run in test. During this test participants will be informed about the standard treatments for mild OSA, and what they can expect if they are randomised to treatment or the control arm of the study.

**Participants who are unable to tolerate CPAP at least an hour will be excluded from participation in the study.**

Following the one hour CPAP trial, baseline demographics such as gender, age, height, and weight, will be collected, along with basic medical history (*Baseline Demographics Form*). During this visit participants will be asked to complete a series of standardised questionnaires (as per Section 10). These questionnaires will be self-administered, although the staff at the site will be available to assist participants with any queries.

At this point participants will be randomised by use of a computer generated randomisation schedule into one of two arms; the CPAP arm or the control arm. Randomisation with minimisation will be used, based on age, BMI and gender (See *Randomisation Schedule*).

## 5.5 CPAP Arm

### 5.5.1 CPAP Initiation

Participants randomised into the CPAP group will be set up on the Auto-adjusting CPAP device (ResMed AirSense S10; response setting for male patients, and AutoSet for Her mode for female patients). The participants will be shown the device and given further instructions on how to use it. They will have the opportunity to try on multiple masks in order to find a mask which is well fitting, comfortable, and unobtrusive. All participants will be provided with humidification to alleviate any discomfort from dry air.

Participants will then take home the device and instructions for use, and will be asked to use the device nightly. As part of the CPAP education participants will be provided with CPAP information and internet links, such as the CPAP user guide, the ResMed youtube channel, and NHS CPAP websites, in order to assist them adapting to CPAP use. Participants will also be shown how to view their nightly usage and mask leak data on their device. Participants with a smart phone will also be introduced to the MyAir App (ResMed). The MyAir app wirelessly downloads data from the device and provides feedback, coaching and tips to patients to assist them with using therapy (see Section 0.) **The MyAir App will not be mandatory in this study, but it will be highly recommended to patients.** If participants are unable to use the MyAir App, they will be shown where to find the equivalent information (CPAP device screen + ResMed websites). This information will also be discussed with them by the Trial Sleep Therapist.

It will be explained that participants device data will be wirelessly monitored on an ongoing basis using the ResMed AirView System (see Section 0) and that the Trial Sleep Therapist may contact them if their data shows that their treatment is not optimal (e.g. their compliance is low, mask leak is high, or AHI is not well controlled).

At this point the participants CPAP details will be entered into the wireless monitoring system (AirView).

### 5.5.2 Phone calls after 3 nights (performed by Trial Sleep Therapist or the local centre)

All participants will be contacted after 3 nights of CPAP use by the Trial Sleep Therapist to discuss their experiences with the PAP treatment and troubleshoot any difficulties that the participant is having. If the participant is having issues which cannot be resolved over the phone they will be invited for an additional clinic visit where the Trial Sleep Therapist may take additional steps such as changing the mask (*Three day phone call CRF*).

These phone calls will be performed by the Trial Sleep Therapist. This person is experienced with the use of CPAP and setting up patients. In order for the advice and care during the study to be consistent, the Trial Sleep Therapist will be responsible for managing the participants during the three- month study. However if the site wish to actively manage the patients themselves, they will be trained to do so by the Trial Sleep Therapist.

If the Trial Sleep Therapist is unable to contact the patient following 3 nights, they may try again after 4 nights and 5 nights. If the Trial Sleep Therapist is still unable to contact the patient during this time they may contact the patient's local sleep service and ask for assistance in contacting the patient.

### 5.5.3 Ongoing monitoring

Participants randomised to the CPAP arm will have their CPAP compliance monitored using the ResMed AirView Remote Monitoring system which accompanies the CPAP devices used in the study (see Section 0.) The Trial Sleep Therapist will be responsible for monitoring all the CPAP data regularly. In order to ensure consistent monitoring and patient follow-up, responsibility of the patient care during the three month study fall to the Trial Sleep Therapist.

The Trial Sleep Therapist will review the data on a regular basis (at least twice per week) and will intervene when compliance is low or other issues are identified. For example, the Trial Sleep Therapist will intervene if they see that for a period of  $\geq 3$  consecutive nights either of the following takes place:

- Compliance is low (<4 hours per night);
- leak is high (>24L/min);
- treatment is not optimal (AHI $\geq 5$ )

In this instance the Trial Sleep Therapist will contact the patient to discuss the issue and potential solutions. Participants will be invited for further clinic visits if required (*CPAP Therapist CRF*). Visits will take place at the participants local sleep service, and will be conducted by the Trial Sleep Therapist. The patient's local sleep service will be informed of any contact and what follow up was taken.

If the participant is unable to be contacted after multiple attempts, the Trial Sleep Therapist will contact the patient's local sleep service and ask for assistance contacting the patient. If contact is still unsuccessful the participant will be withdrawn from the trial and deemed 'lost to follow-up'.

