### 5.6.1 Three day phone call

The control arm will also receive a phone call three days after visit one, to discuss the sleep hygiene behaviors and answer any questions the participant may have. This phone call will be conducted by the Trial Sleep therapist to ensure that all information given to participants is consistent.

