## 5.8 Pilot Phase

In order to test the trial methodology, the trial will start with a pilot phase of 20 randomised participants. At this stage the steering committee will meet to review the following:

- Average CPAP compliance
- Trial methodology and flow

**Compliance to treatment is crucial for study to be able to demonstrate whether CPAP treatment yields improvements in mild patients.** In order for patients to experience quality of life benefits, it has been shown that at least 4 hours usage per night is required, with greater use associated with increased benefits. If, during the pilot phase, average compliance is lower than 4 hours per night, the protocol will be amended to include the use of a CPAP 3 day run in phase, in order to include only patients who are able to use the device for greater than four hours per night. Additional changes to the protocol may also be made based on findings from the pilot phase.

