### 7.5 Handling of Subject withdrawals

Enrolment is completely voluntary and participants are free to withdraw from the study at any time. Subjects who withdraw will continue to visit their local sleep service for routine clinical care. Reason for withdrawal will be documented on the participants CRF.

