4.6 Sample Size

The sample size of 224 (112 per arm) is based on statistics observed in the MOSAIC study: a mean score difference of 6.6 was observed between 3 months and baseline (considered a significant clinical improvement by the authors of the study) in the Energy and Vitality subscale of the SF-36 questionnaire, with a mean change of 4.2 (SD 18.1) in the Control group and 10.8 (SD 17.0) in the CPAP Treatment group. The sample size calculation is based on a two-sided 5% significance level and 80% power.

It is estimated that approximately 300 participants will need to be randomised in order to reach the required sample size of 224 patients with mild OSA **per AASM 2012 guidelines**. Subjects who are eligible for Home Sleep Testing (HST) are evaluated for their level of OSA. Those patients who have Mild OSA **per AASM 2007 guidelines** are eligible for randomisation. Those patients who have No OSA **per AASM 2007 guidelines** are further assessed based on the AASM 2012 guidelines. All patients with

AHI \geq 5 per AASM 2012 guidelines are also eligible for randomisation. Since the primary endpoint analysis is based on patients with mild OSA per AASM 2012 guidelines, there will be some patients randomised who will not fall into this sample, thus the need for additional enrolment. Additionally, it is expected that 10% of those randomised will drop-out before the end of the study.

The number of patients required to enrol will be reviewed and updated by the Trial Steering Committee (TSC) as new recruitment information accumulates. This will not change the goal of 224 patients completing the study who had mild OSA per the AASM 2012 guidelines.

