5. STATISTICAL METHODS

5.1 Study Populations and Analysis Groups

There are two main study populations in this trial, one group fulfilling the mild OSA AASM 2012 guidelines and the second fulfilling the mild OSA AASM 2007 guidelines. Some trial patients will fulfil both criteria and will therefore be eligible for analysis under both AASM 2007 and AASM 2012. A third study population will consist of patients who fall into the category of Moderate to Severe OSA based on the AASM 2012 guidelines. Patients in this third population will either have tested as No OSA (AHI < 5 e/hr) or Mild OSA based on AASM 2007 guidelines.

The primary endpoint analysis will only be conducted on mild OSA patients per AASM 2012 guidelines. Each secondary endpoint analysis will be carried out on mild OSA patients based on AASM 2012 and AASM 2007 guidelines. Additionally, secondary analyses will be generated descriptively for the subgroup of patients with Moderate to Severe OSA per AASM 2012 guidelines. Therefore, all patients randomised into the trial will be analysed in one or more secondary analyses, with a subset of these patients fulfilling the AASM 2012 guidelines and qualifying for the primary analysis.

The intention to treat (ITT) analysis population will include all randomised patients. The ITT population will be further subdivided as follows:

ITT-1 population includes patients in the ITT with mild OSA per AASM 2012 guidelines.

ITT-2 population includes patients in the ITT with mild OSA per AASM 2007 guidelines.

ITT-3 population includes patients in the ITT with moderate to severe OSA per AASM 2012 guidelines.

The primary endpoint analysis, pool-ability analysis (see Section 5.3) and comparability of baseline characteristics will be generated for the ITT-1 population.

The completed cases (CC) analysis population will be a subset of the ITT population that includes patients who complete the 3-month study visit. [It is possible for there to be missing values for one or more outcome measures in the CC group, if a patient who completes the visits does not complete the questionnaires completely.] The CC population will be further subdivided as follows:

CC-1 population includes patients in the CC with mild OSA per AASM 2012 guidelines.

CC-2 population includes patients in the CC with mild OSA per AASM 2007 guidelines.

CC-3 population includes patients in the CC with moderate to severe OSA per AASM 2012 guidelines.

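### A withdrawal rule written only for the CPAP arm may lose obtainable month-3 scores in that arm; follow-up should be governed by one rule for both arms

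*Protocol*

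**What the plan says.** Protocol 5.5.3 (Ongoing monitoring) is part of section 5.5, CPAP Arm. The therapist reviews device data at least twice a week and contacts the patient when there is a problem. The examples given are, over three or more consecutive nights, use below 4 hours, leak above 24 L/min, or AHI of 5 or more. If repeated attempts fail, the local sleep service is asked to help. After that: "If contact is still unsuccessful the participant will be withdrawn from the trial and deemed" lost to follow-up.

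The control arm has no counterpart. Protocol 5.6.1 says "The control arm will also receive a phone call three days after visit one"; there is no monitoring, and no withdrawal follows failed contact. Within the CPAP arm, an unanswered day-3 call (5.5.2) does not lead to withdrawal either.

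On what happens after withdrawal, Protocol 7.5 says "Subjects who withdraw will continue to visit their local sleep service for routine clinical care" and "Reason for withdrawal will be documented on the participants CRF". It does not mention a month-3 questionnaire. Protocol 5.7 asks both arms to attend at three months, but no visible text re-invites a patient already withdrawn.

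In the SAP, section 5.1 states "The intention to treat (ITT) analysis population will include all randomised patients", and ITT-1 is the part of that population with mild OSA by AASM 2012. The primary model (5.7) contains visit, treatment by visit, subject and site. It has no CPAP-usage term and relies on missing at random (5.4). The amendment in SAP section 8 uses ANCOVA with baseline carried forward for the sensitivity and secondary analyses.

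**The concern.** The rule makes failure to answer therapy-support calls the end of outcome collection. These are separate matters: a patient who ignores calls about the device might still return a questionnaire. Because only device data can set the process off, any loss it causes falls in the CPAP arm.

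ITT-1 keeps such a patient's baseline score but cannot supply the missing month-3 score. The primary model in effect assumes that, given baseline, site and arm, the patient would have changed like the rest of the CPAP arm. The protocol's own premise points the other way for low users: on quality of life benefit, section 5.8 says "it has been shown that at least 4 hours usage per night is required". If low users gain less and are the ones lost, the completers' mean is too high and the primary estimate leans towards CPAP. This applies to only part of the group, since leak and residual AHI are also triggers.

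At stake is the size of the treatment estimate in an open-label trial with a patient-reported endpoint.

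**Working it through.** **Inputs (SAP 4.6; Protocol 11.2.1).** Mean change 10.8 (SD 17.0) with CPAP and 4.2 (SD 18.1) in controls; difference 6.6; two-sided 5%; 80% power; 112 per arm. On drop-out, SAP 4.6 adds that "it is expected that 10% of those randomised will drop-out before the end of the study".

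**The plan's own figure.** Pooled SD = √((17.0² + 18.1²)/2) = 17.56. Required n per arm = 2 × (17.56 × (1.960 + 0.842)/6.6)² = 111.1, rounded up to 112, so 224 in total. The stated size reproduces.

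**Reference quantities.** Design SE = √(17.0²/112 + 18.1²/112) = 2.35. Significance threshold = 1.96 × 2.35 = 4.60. SAP 4.6 counts 224 completers, so about 112/0.9 = 124 per arm are randomised.

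**Bias in the primary estimate.** Let a share p of the CPAP arm be lost under 5.5.3. The documents give no count, so p is an assumption. Suppose these patients would have gained 4.2 and the whole-arm mean is 10.8. The mean x of the remaining CPAP patients solves (1 − p)x + 4.2p = 10.8, so the bias is x − 10.8 = 6.6p/(1 − p).

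**Part the fix can remove.** If a share r of these scores is recovered, as a random part of those lost, the bias removed is 6.6p/(1 − p) − 6.6p(1 − r)/(1 − p(1 − r)). The shares r are also assumptions.

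**Offset from control losses.** If the same share of controls is lost and would have gained 0, the control mean rises by 4.2p/(1 − p) (0.09, 0.22, 0.47), which is subtracted from the bias.

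**Baseline carried forward.** With 10% missing in each arm and the other losses at random, the estimate is 0.9x − 0.9 × 4.2.

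| | p = 2% | p = 5% | p = 10% |
|---|---|---|---|
| Patients of 124 | 2–3 | about 6 | about 12 |
| Primary estimate | 6.73 | 6.95 | 7.33 |
| Bias | +0.13 | +0.35 | +0.73 |
| Bias / SE | 0.06 | 0.15 | 0.31 |
| Removed by fix, r = 25% | 0.03 | 0.09 | 0.20 |
| Removed by fix, r = 50% | 0.07 | 0.18 | 0.39 |
| Net bias with equal control loss | 0.05 | 0.13 | 0.27 |
| Baseline carried forward | 6.06 | 6.25 | 6.60 |

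The 10% column is an upper bound that assigns the whole expected drop-out to this one rule.

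**Other assumptions about the lost patients.** If they would have gained 0, the bias is 10.8p/(1 − p) = 0.22, 0.57 and 1.20. If they would have gained 10.8, there is no bias.

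**Power.** With the CPAP arm reduced to 112(1 − p), power at 6.6 is 79.9%, 79.4% and 78.3%, against 80.3% with no loss. The loss is about 2 percentage points at most.

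**Imputing these patients from the control-arm change.** This returns 6.60 at every p if the 4.2 assumption is right. If missing at random holds instead, it gives 6.6 − 6.6p = 6.47, 6.27 and 5.94. It is a lower bracket to read beside the primary estimate.

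**The case against.** The strongest reply is that little can be recovered. The rule applies only after repeated attempts and failed help from the local service, so many of these patients would have no month-3 score under any rule. What the fix can remove is 0.03 to 0.39 points, roughly 0.01 to 0.16 SE, on recovery shares that have no basis in the documents. This stands, and it is why the full bias should not be read as the benefit of the change.

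The direction is conditional. It depends on the 4-hour premise and on low use being the trigger, and the mix of triggers is unknown. This stands too.

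The SAP also has a partial safeguard. In the main scenario above, the primary analysis and the baseline-carried-forward ANCOVA fall on either side of 6.6 at 2% and 5%, and the ANCOVA equals it at 10%. But carrying baseline forward treats every missing score in both arms alike, so it does not isolate what this rule contributed.

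It may also be said that withdrawn status is only a label, that Protocol 7.5 does not forbid a month-3 questionnaire, and that consent wording is not visible. However, 5.5.3 says in terms that the patient leaves the trial, and no visible text restores the questionnaire.

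Finally, follow-up was expected to end on 31 March 2019 (SAP 4.2), and the amendment reports the primary analysis as already performed. The protocol change may come too late, which leaves the reporting remedy.

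**Conclusion.** The concern holds. A written rule can end outcome collection in the CPAP arm alone, and the primary analysis has no means of correcting for it if the lost patients gain less than the rest of their arm given baseline. Only the written rule is one-sided; controls can still be lost for other reasons.

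If the lost patients would have gained 4.2, the primary estimate is too high by 0.13, 0.35 or 0.73 points at losses of 2%, 5% or 10%, and the avoidable part is smaller. At the design effect the estimate stands 6.6 − 4.6 = 2.0 points above the significance threshold, so the verdict on significance does not change; the effect is on the size of the estimate.

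All loss rates, recovery shares and unseen gains are assumptions. Points are on the planning scale, whereas SAP 4.8 presents SF-36 scores as norm-based; the ratios to the SE carry over if gains and SDs rescale together. The change is worth making because it is cheap and removes an avoidable asymmetry. Confidence is medium.

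**What to change.** **If follow-up is still open.** Amend the last sentence of Protocol 5.5.3 so that failed contact is recorded and the patient stays in follow-up unless consent is withdrawn. Under one rule for both arms, seek the month-3 visit or, failing that, posted questionnaires. The post is feasible because Protocol 5.4.1 says "These questionnaires will be self-administered, although the staff at the site will be available to assist participants with any queries". Record a patient as lost to follow-up only when no month-3 data are obtained. Contact triggers and care are unchanged. The cost is a one-sentence amendment with its approval and a few letters or calls at month 3.

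**If data collection is complete.** Where the records allow, show withdrawals under 5.5.3 as a separate reason in the withdrawal table already planned (SAP 5.5 and 7). The CRF withdrawal reason (Protocol 7.5) and the missed-contact records (SAP 5.10) may identify them. The SAP amendment defers reporting of contact details to a later paper, so those records would need to be consulted for this purpose now.

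Add one ITT-1 sensitivity analysis of the primary endpoint, labelled post hoc. It imputes these patients' month-3 scores from the control-arm change given baseline, and all other missing scores in both arms under missing at random. A no-change scenario is already largely covered by the baseline-carried-forward analysis. The cost is one table row and one analysis. If these withdrawals cannot be told apart from other CPAP-arm losses, the report should say so.
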